8.4.4 QMG score

The QMG scores and change from Baseline will be summarized by treatment group, RLZ total and visit using descriptive statistics. The subgroup summaries will also be performed by MG-specific autoantibody (MuSK+ or AChR+) and by administered dose for each weight subgroup as specified in [Section 4.9.1](#) and [Section 4.9.3](#).

The QMG score (excluding ocular items) change from Baseline will be calculated the same as the change from Baseline in the QMG score. The QMG scores (excluding ocular items) and change from Baseline will be summarized by treatment group, RLZ total and visit using descriptive statistics.

Above QMG summaries will be repeated for COVID-19 free participants, where COVID-19 free participants exclude:

- Participants who discontinue treatment due to suspected/confirmed COVID-19 infection (“Confirmed COVID-19” or “Suspected COVID-19” as the relationship to COVID-19 in the COVID-19 Impact eCRF);
- Participants who discontinue treatment due to non-infection related COVID-19 issues (“General circumstances around COVID-19 without infection” or “other” as the relationship to COVID-19 in the COVID-19 Impact eCRF);

- Participants have visits affected in treatment period (e.g. visit performed by video call) due to COVID-19.

A boxplot of change from Baseline at Day 43 and a time plot of mean change and percentage change from Baseline for QMG will also be plotted by the following dose groups: placebo, [REDACTED].

By-participant listings of QMG scores will be provided.

8.4.5 QMG responder rate (≥ 3.0 points improvement from Baseline)

Study participants will be classified as responders at a visit if the value is at least a 3-point improvement (decrease) from Baseline. Missing data will be imputed using NRI per [Section 4.2.1](#).

The number and percentage of observed and imputed responders will be summarized separately by treatment group, RLZ total and visit. In addition, QMG responders will be summarized by MG-specific autoantibody (MuSK+ or AChR+) and by administered dose for each weight subgroup as specified in [Section 4.9.1](#) and [Section 4.9.3](#). Same summaries will be repeated for COVID-19 free participants as defined in [Section 8.4.4](#).

8.4.6 MG-C score

The total scores and total score (excluding ocular items) with associated change from Baseline will be summarized by treatment group and RLZ total at scheduled visit using descriptive statistics. The subgroup summaries will also be performed by MG-specific autoantibody (MuSK+ or AChR+) and by administered dose for each weight subgroup as specified in [Section 4.9.1](#) and [Section 4.9.3](#). Same summaries will be repeated for COVID-19 free participants as defined in [Section 8.4.4](#).

A boxplot of change from Baseline at Day 43 and a time plot of mean change and percentage change from Baseline for MG-C will also be plotted by the following dose groups: placebo, [REDACTED].

By-participant listings of MG-C scores will be provided.

8.4.7 MG-C responder rate (≥ 3.0 points improvement from Baseline)

Participants will be classified as responders at a visit if the value is at least a 3-point improvement (decrease) from Baseline (Burns, Ted M et al [2010]). Missing data will be imputed using NRI per [Section 4.2.1](#).

The number and percentage of observed and imputed responders will be summarized separately by treatment group, RLZ total and visit. In addition, MG-C responders will be summarized by MG-specific autoantibody (MuSK+ or AChR+) and by administered dose for each weight subgroup as specified in [Section 4.9.1](#) and [Section 4.9.3](#). Same summaries will be repeated for COVID-19 free participants as defined in [Section 8.4.4](#).

8.4.8 MG-ADL score

See [Section 8.2.1](#) for the derivation of MG-ADL total score.

The MG-ADL scores and change from Baseline will be summarized by treatment group, RLZ total and visit using descriptive statistics. The subgroup summaries will also be performed by

subgroups in [Section 4.9.1](#) and by administered dose for each weight subgroup as specified in [Section 4.9.3](#).

The MG-ADL score (excluding ocular items) change from Baseline will be calculated the same as the change from Baseline in the MG-ADL score. The MG-ADL scores (excluding ocular items) and change from Baseline will be summarized by treatment group, RLZ total and visit using descriptive statistics.

The mean change from Baseline with 95% CI in MG-ADL total score over time with cumulative ADA or NAb status will be plotted by treatment group and RLZ total. See details in [Section Error! Reference source not found.](#)

A boxplot of change from Baseline at Day 43 and a time plot of mean change and percentage change from Baseline for MG-ADL will also be plotted by the following dose groups: placebo,

The study participants with missing MG-ADL assessment and associated reasons at each scheduled visit will be summarized by treatment group and RLZ total. Same summaries will be repeated for COVID-19 free participants as defined in [Section 8.4.4](#).

By-participant listings of MG-ADL values will be provided.

8.4.9 MG-ADL responder rate (≥ 2.0 points improvement from Baseline)

Derivation of the responder is detailed in [Section 8.3.1](#).

The number and percentage of observed and imputed responders will be summarized separately by treatment group, RLZ total and visit. In addition, MG-ADL responders will be summarized by subgroups in [Section 4.9.1](#) and by administered dose for each weight subgroup as specified in [Section 4.9.3](#). Same summaries will be repeated for COVID-19 free participants as defined in [Section 8.4.4](#).

8.4.10 MG Symptoms PRO 'Physical Fatigue' score

See [Section 8.3.5](#) for the derivation of MG Symptoms PRO 'Physical Fatigue' score.

The PRO Physical Fatigue scores and change from Baseline will be summarized by treatment group, RLZ total and visit using descriptive statistics. The subgroup summaries will also be performed by MG-specific autoantibody (MuSK+ or AChR+) and by administered dose for each weight subgroup as specified in [Section 4.9.1](#) and [Section 4.9.3](#).

In addition, empirical cumulative distribution functions of the change in score from Baseline to Day 43 will be plotted by treatment group and RLZ total.

By-participant listings of all MG Symptoms PRO values will be provided.

8.4.11 MG Symptoms PRO 'Muscle Weakness Fatigability'

See [Section 8.3.4](#) for the derivation of MG Symptoms PRO 'Muscle Weakness Fatigability' score.

The PRO Muscle Weakness Fatigability scores and change from Baseline will be summarized by treatment group, RLZ total and visit using descriptive statistics. The subgroup summaries will also be performed by MG-specific autoantibody (MuSK+ or AChR+) and by administered dose for each weight subgroup as specified in [Section 4.9.1](#) and [Section 4.9.3](#).

In addition, empirical cumulative distribution functions of the change in score from Baseline to Day 43 will be plotted by treatment group and RLZ total.

8.4.12 MG Symptoms PRO ‘Bulbar Symptoms’

See [Section 8.3.6](#) for the derivation of MG Symptoms PRO ‘Bulbar Symptoms’ score.

The PRO Bulbar Symptoms scores and change from Baseline will be summarized by treatment group, RLZ total and visit using descriptive statistics. The subgroup summaries will also be performed by MG-specific autoantibody (MuSK+ or AChR+) and by administered dose for each weight subgroup as specified in [Section 4.9.1](#) and [Section 4.9.3](#).

In addition, empirical cumulative distribution functions of the change in score from Baseline to Day 43 will be plotted by treatment group and RLZ total.

8.4.13 Patient Global Impressions of Severity

A frequency table will be produced to summarize answers provided to the PGI-S (“none,” “mild,” “moderate,” “severe,” “very severe,”) for each visit by treatment group and RLZ total.

A by-participant listing of PGI-S will be provided.

8.4.14 Patient Global Impressions of Change

A frequency table will be produced to summarize answers provided to the PGI-C (“very much improved,” “much improved,” “minimally improved,” “no change,” “minimally worse,” “much worse,” or “very much worse”) for each visit by treatment group and RLZ total.

A by-participant listing of PGI-C will be provided.

8.4.15 MGII overall scores, ocular sub-scores, and generalized domain scores

The complete list of MGII items and scores are provided in [Table 13-8](#). The total score will be calculated according to the rules set down in [Section 13.5](#).

Summary statistics of the actual values and change from Baseline values will be used to summarize the MGII overall score and sub-scores separately by treatment group and RLZ total for each visit during Treatment period.

A by-participant listing of MGII scores will be provided.

8.4.16 MG-QOL15r

The total score is calculated by summing all the individual items. See [Section 13.6](#) for scoring details.

Summary statistics of the actual values and change from Baseline values will be used to summarize MG-QOL15r scores by treatment group and RLZ total for each visit.

A by-participant listing of MG-QOL15r scores will be provided.

8.4.17 EQ-5D-5L

The EQ-5D-5L essentially consists of 2 pages: the EQ-5D descriptive system and the EQ visual analogue scale (EQ VAS).

A frequency table will be produced to summarize answers provided to each of the 5 dimensions of the EQ-5D descriptive system at each scheduled visit by treatment group. The observed values of EQ VAS scores and change from Baseline will be summarized by treatment group and RLZ total at each scheduled visit. No imputation will be applied on missing item in EQ-5D descriptive system and EQ VAS.

A by-participant listings of EQ-5D-5L will be provided.

8.4.18 Minimal symptom expression

Minimum Symptom Expression (MSE) is designed to assess how many study participants become free or virtually free of MG symptoms as measured by achieving an MG-ADL total score of 0 or 1 (Vissing et al. 2020). See [Section 8.2.1](#) for the derivation of MG-ADL total score.

The number and percentage of study participants achieving MSE at any time during the treatment and observation phases will be summarized by treatment group and RLZ total.

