Participants have the opportunity to rollover into an OLE study, as described below. The OLE study, MG0004 (52-week chronic treatment) will be replaced by MG0007, which consists of 6-week treatment cycles based on MG worsening. Upon study site approval of MG0007, as well as fulfilment of regulatory requirements, study participants will have the opportunity to rollover directly into MG0007. In the event a study participant has already started MG0004, a minimum treatment duration of 6 visits (if IMP treatment is held for low IgG, study participants missed dose(s) can be counted as part of the total 6 visits for completion of MG0004 and meet eligibility requirements for MG0007) must be completed prior to moving into MG0007. Once the site is active for MG0007, no further participants will enroll in MG0004 and the study will be closed at the site once all eligible study participants have discontinued MG0004 and had the opportunity to rollover into MG0007.

The study is composed of a Screening Period of up to 4 weeks, followed by a 6-week double-blind Treatment Period and a blinded Observation Period of 8 weeks:

- All study participants who complete the 6-week Treatment Period will roll over into an 8-week Observation Period.
- All eligible study participants who complete the Observation Period will be invited to be re-randomized into an open-label extension (OLE) study.
- Study participants who experience disease worsening during the 6-week Treatment Period (eg, an increase of 2 points on the MG-ADL or 3 points on the QMG scale between two consecutive visits) may be considered for rescue therapy (IVIg or PEX) at the discretion of the Investigator.
- Study participants who need rescue therapy during the 6-week Treatment Period will receive IVIg or PEX and complete any subsequent visit(s). No further infusions of IMP in MG0003

will be administered after initiation of rescue therapy. Once the participant completes the premature end of treatment (PEOT) Visit (Visit 10), he or she will move into the 8-week Observation Period.

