	
assessment during Treatment and Observation Periods
 
• Change from Baseline in the MG Symptoms PRO ‘Physical Fatigue’ score at each scheduled assessment during Treatment and Observation Periods• Change from Baseline in the MG Symptoms PRO ‘Bulbar Symptoms’ score at each scheduled assessment during Treatment and Observation Periods• Change from Baseline in the MG Symptoms PRO ‘Respiratory Symptoms’ score at each scheduled assessment during Treatment and Observation Periods• Change from Baseline in the MG Symptoms PRO ‘Ocular Symptoms’ score at each scheduled assessment during Treatment and Observation Periods• Change from Baseline in Patient Global Impressions of Severity (PGI-S) at each scheduled assessment during the Treatment and Observation Periods• Patient Global Impressions of Change (PGI-C) at each scheduled assessment during Treatment and Observation Periods• Change from Baseline in MG-ADL (excluding ocular items) at each scheduled assessment during Treatment and Observation Periods• Change from Baseline in QMG (excluding ocular items) at each scheduled assessment during Treatment and Observation Periods• Change from Baseline in MG-C score (excluding ocular items) at each scheduled assessment during Treatment and Observation Periods• Change from Baseline to Day 43 (Visit 10) in MG-QOL 15r
--	---

This document cannot be used to support any marketing authorization applications or variations thereof.

	
 • Change from Baseline to Day 43 (Visit 10) in EuroQol(EQ)-5D-5L • Minimal symptom expression (MG-ADL score of 0 or 1) at any time up to and including Day 43 (Visit 10) • Change from Baseline in MG Impairment Index (MGII) scores at each scheduled assessment during Treatment Period • Change from Baseline in MGII ocular sub-scores at each scheduled assessment during Treatment Period • Change from Baseline in MGII generalized domain sub-scores at each scheduled assessment during Treatment Period

Secondary
	

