2.2.1.3 Other efficacy endpoints

- Use of rescue therapy due to worsening (IVIg, PEX)
- Time to first rescue therapy
- Time to MG-ADL response (≥ 2.0 points improvement from Baseline)
- Change from Baseline in QMG at each scheduled assessment during Treatment and Observation Periods
- QMG responder (≥ 3.0 points improvement from Baseline) at each scheduled assessment during Treatment and Observation Periods
- Change from Baseline in MG-C score at each scheduled assessment during Treatment and Observation Periods
- MG-C responder (≥ 3.0 points improvement from Baseline) at each scheduled assessment during Treatment and Observation Periods
- MG-ADL responder (≥ 2.0 points improvement from Baseline) at each scheduled assessment during Treatment and Observation Periods
- Change from Baseline in the MG Symptoms PRO 'Muscle Weakness Fatigability' score at each scheduled assessment during Treatment and Observation Periods
- Change from Baseline in the MG Symptoms PRO 'Physical Fatigue' score at each scheduled assessment during Treatment and Observation Periods
- Change from Baseline in the MG Symptoms PRO 'Bulbar Symptoms' score at each scheduled assessment during Treatment and Observation Periods
- Change from Baseline in the MG Symptoms PRO 'Respiratory Symptoms' score at each scheduled assessment during Treatment and Observation Periods
- Change from Baseline in the MG Symptoms PRO 'Ocular Symptoms' score at each scheduled assessment during Treatment and Observation Periods
- Patient Global Impressions of Severity (PGI-S) at each scheduled assessment during the Treatment and Observation Periods

- Patient Global Impressions of Change (PGI-C) at each scheduled assessment during Treatment and Observation Periods
- Change from Baseline in MG-ADL (excluding ocular items) at each scheduled assessment during Treatment and Observation Periods
- Change from Baseline in QMG (excluding ocular items) at each scheduled assessment during Treatment and Observation Periods
- Change from Baseline in MG-C score (excluding ocular items) at each scheduled assessment during Treatment and Observation Periods
- Change from Baseline to Day 43 in MG Quality of Life 15 Item scale revised (MG-QOL15r)
- Change from Baseline to Day 43 in Euro-Quality of Life 5-Dimensions, 5 levels (EQ-5D-5L)
- Minimal Symptom Expression (MG-ADL score of 0 or 1) at any time up to and including Day 43 (Visit 10)

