3.9 Changes to protocol-defined analyses

- Mixed model for repeated measures (MMRM) analysis of covariance (ANCOVA) is specified as the model used for the analysis of primary endpoint. In the SAS, MMRM is used as the model only.
- ADDPLAN MC is specified in the protocol for making determinations from the interim analysis. However, SAS or the R package for Adaptive Clinical Trials (RPACT) will be used instead. For the purposes of this analysis, these packages will provide the same functions as ADDPLAN MC.

- The treatment group by week interaction term is specified to be used in the model of analysis of primary efficacy endpoint. In the SAP, treatment group by day interaction will be used instead.
- The Full Analysis Set (FAS) will consist of all study participants in the RS, who have a baseline and at least one post-Baseline MG-ADL measurement. The protocol incorrectly states this as SS.
- Stratification factors used in statistical modeling, such as muscle specific kinase [MuSK(+/-)] and acetylcholine receptor [AChR(+/-)] are defined in the SAP as two binary variables, instead of one binary variable [MuSK(+) or AChR(+)] – this is to account for study participants who may be double-positive.
- Estimands and Intercurrent event handling strategies have been updated based on regulatory feedback.
- Minimal Symptom Expression (MG-ADL score of 0 or 1) at any time up to and include both treatment and observation phase, where the protocol only states to include up to Day 43 (Visit10).
- Potential Hy's Law has been updated to Alanine Aminotransferase (ALT) or Aspartate Aminotransferase (AST) > 3x Upper Limit of Normal (ULN) and total Bilirubin (TBL) > 2x ULN, and Alkaline Phosphatase (ALP) < 2x ULN.
- Calculation of Low-density lipoprotein (LDL) will follow Friedewald equation, where LDL in mmol/L = TC - HDL - TRIG/2.22; LDL in mg/dL = LDL = TC - HDL - TRIG/5 (if all values are in mg/dL). This formula is applicable only if Triglycerides is less than or equal to 400 mg/dL (4.52 mmol/L).
- MG-C responders are defined as at least a 3-point improvement (decrease) from Baseline instead of 5-point improvement.
- Patient Global Impressions of Severity (PGI-S) at each scheduled assessment during the Treatment and Observation Periods instead of change from Baseline of PGI-S.

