8.2.2 Primary analysis of the primary efficacy endpoint

The primary analysis is based on the RS under the hypothetical & treatment policy strategy (see details in [Section 8.1](#)). Any missing MG-ADL scores (including missing data after the intercurrent events) will be handled based on maximum likelihood estimation method under MAR assumption.

A stage-wise MMRM with treatment group, Baseline MG-ADL score, region, stratification factor(s) including MuSK(+/-) and /or AChR(+/-), and treatment group by day (interaction term) as fixed factors and study participant as a random effect. The MMRM will include Days 8, 15, 22, 29, 36 and 43.

The model will utilize an unstructured covariance pattern for the repeated measures. If the model does not converge using the unstructured pattern, then an autoregressive covariance structure

will be used. The Kenward-Roger approximation will be used to estimate the denominator degrees of freedom.

For each stage, the least squares means (LSMs) of each treatment group, and the least squares mean differences (LSMDs) between each dose group and placebo will be reported for Day 43 (Visit 10), along with the corresponding 2-sided 97.5% CIs and p-values.

The study follows a 2-stage group sequential adaptive design using combination test (Lehmacher and Wassmer, 1999) based on the inverse-normal method of combining independent stagewise p-values (Hedges and Olkin, 1985)

The analysis takes into account that the study is a 2-stage group sequential adaptive design assuming equal weighting of each stage, with weights = $1/\sqrt{2}$:

- Stage 1 – Cohort up to the formal IA
- Stage 2 – Cohort post-IA

The following sequential test statistic will be used to test the global null hypothesis at the end of stage 2:

$$T = \sum_{i=1}^2 w_i \phi^{-1}(1 - p_i)$$

Where subscript $i = 1, 2$ represents the stage, p_i represents the appropriate multiplicity adjusted p-value at stage i (for example at stage 1, $p_1 = \min(2 * p_{\min}, 1)$ where p_{\min} is the minimum of the two nominal p-values), the weights $w_{ki} = 1/\sqrt{2}$ satisfy $\sum_{i=1}^2 w_{ki}^2 = 1$ and ϕ^{-1} is the inverse cumulative standard normal distribution function. The test statistic T and $z = \phi^{-1}(1 - p_i)$ have a standard normal distribution, (Lehmacher and Wassmer, 1999).

The combined p-value (2-sided) for the 2 stages, which tests the global null hypothesis, can be calculated by:

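### SAP 8.4.18 tabulates minimal symptom expression only over treatment plus observation, so the Day 43 endpoint that both documents define is never reported

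*SAP*

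**What the plan says.** The two endpoint lists agree. Protocol Table 3-1, like the synopsis, has "Minimal symptom expression (MG-ADL score of 0 or 1) at any time up to and including Day 43 (Visit 10"), and SAP 2.2.1.3 has "Minimal Symptom Expression (MG-ADL score of 0 or 1) at any time up to and including Day 43 (Visit 10").

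The SAP's analysis text departs from this. Section 3.9, which lists changes from the protocol, sets the window as "at any time up to and include both treatment and observation phase" and notes that the protocol goes only to Day 43. Section 8.4.18 then gives the only output: the number and percentage "achieving MSE at any time during the treatment and observation phases", shown for each treatment group and for rozanolixizumab in total. It has no Day 43 row.

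Two other SAP provisions bear on this endpoint. Section 8.4 makes the other efficacy variables descriptive unless stated otherwise. Section 4.2.1 treats other binary efficacy endpoints as non-response when data are missing at the timepoint of interest and at every timepoint after rescue. Section 8.4.18 does not repeat that rule.

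**The concern.** A programmer working from 8.4.18 produces one MSE percentage per arm. A reader who looks up the endpoint in the protocol or in SAP 2.2.1.3 will take it as symptom freedom reached by the end of the treatment course. It is not that. A participant in any arm who first scores 0 or 1 on Day 85, seven weeks after the last scheduled dose on Day 36, is counted.

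Whether a participant becomes virtually symptom-free by Day 43 and whether this happens at some point in the following eight weeks are different questions. As planned, one number answers a mixture of the two, and the number that answers the defined question does not appear.

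**Working it through.** **Windows side by side**

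| Place | Window |
|---|---|
| Protocol synopsis and Table 3-1 | up to and including Day 43 |
| SAP 2.2.1.3 | up to and including Day 43 |
| SAP 3.9 | treatment and observation, declared as a change |
| SAP 8.4.18 (the only output) | treatment and observation |

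Neither 3.9 nor 8.4.18 says why the window was widened.

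**Number of looks.** The protocol's Schedule of Activities (1.3) places MG-ADL after Baseline at V4, V5, V6, V8, V9 and V10. SAP 8.2.2 confirms these six: "The MMRM will include Days 8, 15, 22, 29, 36 and 43". The schedule then adds V11 to V14 on Days 57, 71, 85 and 99. So 6 + 4 = 10. The added visits fall 57 − 43 = 14 to 99 − 43 = 56 days after Visit 10. The last scheduled dose is on Day 36 (V9), so they also fall 21 to 63 days after it.

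**Effect on each arm's percentage.** The documents state no MSE rate, so there is no plan figure to reproduce and everything below rests on assumptions. An any-time criterion over 10 visits includes every participant who meets it over the first 6, so the proportion cannot fall. For its size with no drug effect, 400,000 participants per setting were simulated. The true score had mean 7 to 8 and SD 3, the observed score had to be at least 3 at V1 and V2, and each visit's score was rounded and clipped to 0–24.

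| Setting | 6 looks | 10 looks |
|---|---|---|
| Mean 8, visit noise SD 1.5 | 2.8% | 4.0% |
| Mean 7, visit noise SD 1.5 | 4.5% | 6.4% |
| Range over noise SD 1 to 2 | 1.0%–8.9% | 1.4%–12.3% |

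**Effect on the between-arm difference.** A simple model shows that its direction is open. Take independent visits with an assumed per-visit chance p of a score of 0 or 1: 2% on placebo and 5% on active drug to Day 43. The chance of at least one such score in k visits is 1 − (1 − p)^k.

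- To Day 43: placebo 1 − 0.98^6 = 11.4%, active 1 − 0.95^6 = 26.5%, difference 15.1 points.
- Ten visits, active returning to the placebo rate off drug: placebo 1 − 0.98^10 = 18.3%, active 1 − 0.95^6 × 0.98^4 = 32.2%, difference 13.9 points.
- Ten visits, active effect persisting: active 1 − 0.95^10 = 40.1%, difference 21.8 points.

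The simulation gives the same picture at mean 8 and noise 1.5. With an on-drug effect of 2.5 points fading to zero by V13, the active rate goes from 16.0% to 16.8%. The difference goes from 16.0 − 2.8 = 13.2 to 16.8 − 4.0 = 12.8 points, a loss of 0.4. Repeat runs with a slightly different on-drug build-up moved the difference from 12.7 to 13.3 under a slower fade, and from 12.9 to 17.6 with full persistence.

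**Unequal looks.** Under protocol 4.1, a participant who completes treatment and then needs rescue during observation may complete the end-of-study visit and move at once to the open-label study. That participant loses any remaining observation visits, so the number of added looks can depend on outcome. The documents give no rate for this, so it cannot be sized.

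**The case against.** The strongest reply is that this is a declared change and not a slip. Section 3.9 exists to record departures, and its bullet names the protocol's Day 43 limit. The protocol describes "followed by a 6-week double-blind Treatment Period and a blinded Observation Period of 8 weeks", and section 4.2 says that the Observation Period is partly for following how long clinical effects last. An MSE summary across it is a reasonable descriptive choice. Nothing inferential depends on MSE, which lies outside the testing hierarchy. A Day 43 figure could also be recovered from the by-participant MG-ADL listings planned in SAP 8.4.8. All of this stands. It limits the weight of the point, but it does not reconcile 2.2.1.3 with 8.4.18 or supply the missing row.

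A reader might infer three stronger things that the documents do not support:

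- **That the extra chances are credited to rozanolixizumab.** Placebo participants have the same four scheduled visits, so every arm's proportion can rise.
- **That the longer window dilutes the contrast.** This needs an assumed fade. Under that assumption the simulated loss is 0.4 points, or 0.004 × 80 ≈ 0.3 of a participant at the cap of 80 per arm, and a slower fade or a persistent effect widens the contrast.
- **That the SAP weakened the criterion by accepting one unconfirmed score.** The protocol's any-time definition already does so. The SAP adds looks only.

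The rescue rule in SAP 4.2.1 probably already stops scores after IVIg or PEX from counting. Because it is worded by timepoint and 8.4.18 is silent, its use for an any-time endpoint should be stated.

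**Conclusion.** The point holds as a documentary inconsistency with a small numerical consequence. The SAP carries two windows for one endpoint, gives no reason for the change, and never tabulates the version that both endpoint lists define.

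That the proportion in each arm stays the same or rises follows from the definition. The increase from about 2.8% to 4.0% with no effect rests on the assumed mean, SD and visit noise. The direction of change in the between-arm difference is not determined, because the documents give no off-drug course for MG-ADL. Outcome-dependent loss of observation visits is possible but cannot be sized.

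MSE is descriptive and has no alpha, so this is a minor correction. It is worth making because it changes a reported percentage at almost no cost.

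**What to change.** In SAP 8.4.18:

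- Report MSE over Visits 4 to 10 (to Day 43) as the defined endpoint.
- Show the treatment-plus-observation result, or an observation-only result, as a separately labelled row. The observation summary need not be dropped.
- State that the 4.2.1 non-response rule for timepoints after rescue applies.

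Then reconcile 2.2.1.3, 3.9 and 8.4.18 so that each names the same windows, and give a reason in 3.9 for the added summary.

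The cost is a few sentences and one extra table row. The headline MSE percentage may be slightly lower than under the present text.
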